1. DESIGN

Design overview

Cardiac murmurs in children: Predictive value of cardiac markers (CAMUS) is an observational study on spontaneously discovered cardiac murmurs in children. The primary aim is to establish the predictive value of cardiac markers for identification of cardiac disease in children with heart murmurs. NT-proBNP and hs-troponins are considered the most relevant cardiac markers. Secondary aims are: a) To establish age-adjusted reference range for cardiac markers in children, and b) To explore aspects of cardiovascular physiology in children.

In part 1 of the project, a total of ~500 individuals aged 4 weeks to 10 years will be consecutively recruited among those referred to the Dept. of Paediatrics and Adolescent Medicine, Akershus University Hospital (Ahus) for assessment of heart murmurs. The protocolized investigational program of the study includes clinical examination, symptom assessment, pulse oximetry, blood sampling, ECG recording, and echocardiography. A definite diagnosis of cardiac disease or not will be based upon the echocardiographic examination, hence serving as the “gold standard”.

In part 2 of the project, a total of ~125 individuals aged 4 weeks to 10 years with confirmed congenital heart disease (CHD) and scheduled for intervention at OUS Rikshospitalet will be included. They will undergo the same investigational program as in part 1. A main purpose of part 2 is to validate the prediction model developed in part 1.

Table 1. Criteria for inclusion and exclusion

Inclusion criteria	Exclusion criteria
Spontaneously discovered heart murmur at general practitioner's office (part 1)	Known cardiac disease (part 1 only)
Confirmed cardiac anomaly and scheduled for intervention at OUS Rikshospitalet (part 2)	Other chronic or acute disorder (part 1 only)
Age > 4 weeks, < 10 years	Medications (part 1 only)

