4. SAMPLE SIZE CONSIDERATIONS

The value of possible predictors will be assessed through the construction of Receiver Operating Characteristics (ROC) curves, and calculation of negative predictive value. Based upon register data from the outpatient clinical at Ahus, the prevalence of cardiac disorder in the population under study is estimated at 2 %. The area under the ROC-curve for NT-proBNP in a previous study with similar methodology has been established at 0.85 (Law et al, 2009). The possible clinical application of the results from the present study requires a very low risk of false negatives (ie. no patients with cardiac disorders should be deemed healthy based upon a certain cardiac marker). Therefore, the level of significance (α) is set to 0.01. Given a test power ($1 - \beta$) = 0.8, sample size is estimated at 400 patients. A drop-out rate of up to 20 % might be assumed (technical problems, refusal of blood sampling, etc), therefore a total of 500 patients should be included in the study.

In part 2, when a population of 125 patients with well-defined CHD is added to the population of about 500 individuals previously recruited, the ratio of cases:controls increases to about 0.25. This will enable an α -value less than 1×10^{-10} , and a power ($1 - \beta$) of comparable magnitude, which we find satisfactory.

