6. STATISTICAL METHODS

General considerations

Continuous variables will be reported with parametric (mean/standard deviation) or non-parametric (median, quartiles) descriptive statistics, depending on the distribution. Ordinal/nominal variables will be reported as frequency tabulation. All statistical tests will be carried out two-sided. A p-value ≤ 0.05 is considered statistically significant throughout.

Predictor analysis

In part 1, the relationship between each potential predictor variable and the primary outcome variable will first be explored in univariate logistic regression analyses. Collinearity between predictor variables will be assessed by correlation analyses, and dimensionality reduction by PCA will eventually be considered. Then, all variables with a p-value ≤ 0.25 in the univariable analyses will be included in the first modelling step. In order to obtain a more parsimonious model, the combination of variables that gives the lowest Akaike Information Criteria (AIC) will constitute the final model. The value of predictor(s) in the final multivariable model will be assessed through the construction of Receiver Operating Characteristics (ROC) curves, and calculation of negative predictive value.

In part 2, the prediction model from part one will be validated by including a total of n~125 individuals with known CHD in the study population. The prediction model should correctly classify all these cases; if not, the model will be adjusted. We aim for zero false negatives, i.e. all cases with cardiac abnormalities in need of intervention and/or hospital follow-up should be identified. To explore the potential of the prediction model to classify all cases based upon this premise, we will apply different combinations of levels of the identified predictor variables.

Cross-sectional analyses

For the secondary study aims, cross-sectional analyses across cases and controls are feasible. Such analyses will feature parametric tests (Student t), non-parametric tests (Mann-Whitney), regression analyses or table analyses (Chi-square, Fisher) as appropriate.

Sensitivity analyses

Throughout, sensitivity analyses applying a different classification of caseness in the primary outcome variable will be carried out:

1. Caseness defined as all abnormalities identified by echocardiography, independent of intervention/follow-up needs
2. Caseness defined as all abnormalities in need of surgical or catheter-based intervention

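### Part 2 is meant to validate the Part 1 model, but the model is adjusted on the same cases if any is missed, with no cutoff, lock or first-pass report fixed beforehand

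*SAP*

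**What the plan says.** Section 1 of the SAP (Design) states: "A main purpose of part 2 is to validate the prediction model developed in part 1". Section 6 (Predictor analysis) describes the sequence.

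- **Part 1.** Predictors are screened at a univariable p-value of 0.25 or less, after which "the combination of variables that gives the lowest Akaike Information Criteria (AIC) will constitute the final model". On performance, "The value of predictor(s) in the final multivariable model will be assessed through the construction of Receiver Operating Characteristics (ROC) curves", together with the negative predictive value (NPV). No probability or marker cutoff is named.
- **Part 2.** The Part 1 model "will be validated by including a total of n~125 individuals with known CHD in the study population". The next sentence gives the rule at issue: "The prediction model should correctly classify all these cases; if not, the model will be adjusted".
- **Target and means.** The SAP says "We aim for zero false negatives", and that, to explore whether the model can reach this, "we will apply different combinations of levels of the identified predictor variables".

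Section 2 assigns every Part 2 participant as a case. Section 4 says that "the prevalence of cardiac disorder in the population under study is estimated at 2" per cent, which applies to Part 1.

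**The concern.** A validation asks how a fixed model performs in patients who had no part in building it. Here, a single miss among the validation patients leads to a change in the model, and the changed model can only be judged in the same patients, because no others are planned. If it then finds all of them, that shows the tuning met its target. It does not show how many new cases the model would find.

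Four omissions add to this. Without a cutoff, correct classification has no set meaning when the Part 2 data are opened. Nothing locks the model beforehand. Neither the manner of adjustment nor the set of predictor levels to be tried is given. Nothing commits the authors to reporting the unadjusted result.

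The quantity at stake is sensitivity. Section 4 requires a very low risk of false negatives before any clinical use, so readers will rely on this figure most.

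**Working it through.** **1. Number of cases in Part 1.** The plan's sample size reproduces. Inputs from section 4: AUC 0.85, prevalence 2% (49 controls per case), α = 0.01, power 0.80. Section 6 makes tests two-sided. The null AUC of 0.5 is an assumption, because the SAP does not state it. With the Hanley-McNeil variance, n₁·Var ≈ (Q₁ − A²)/49 + (Q₂ − A²), where Q₁ = A/(2 − A) and Q₂ = 2A²/(1 + A):

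- A = 0.5: 0.0833/49 + 0.0833 = 0.0850
- A = 0.85: 0.0166/49 + 0.0586 = 0.0589
- Cases needed = [(2.576·√0.0850 + 0.842·√0.0589)/0.35]² = 7.45, rounded up to 8
- N = 8 × 50 = 400, and 400/0.80 = 500

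Part 1 therefore expects about 2% × 500 = 10 cases, or 2% × 400 = 8 after drop-out.

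**2. How often the adjustment rule would be triggered.** For an unchanged model with true sensitivity s in Part 2 cases, P(at least one miss in 125) = 1 − s¹²⁵:

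- s = 95%: 1 − 0.0016 = 99.8%
- s = 98%: 1 − 0.0800 = 92.0%
- s = 99%: 1 − 0.2847 = 71.5%
- s = 99.5%: 1 − 0.5344 = 46.6%
- s = 99.9%: 1 − 0.8824 = 11.8%

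An even chance of no adjustment needs s = 0.5^(1/125) = 0.9945.

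**3. What an unadjusted first pass would be worth.** Exact (Clopper-Pearson) 95% limits; with no misses in n, the lower limit is 0.025^(1/n):

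- 125/125: lower limit 0.025^(1/125) = 97.1%
- 10/10: lower limit 0.025^(1/10) = 69.2%
- 8/8: lower limit 0.025^(1/8) = 63.1%
- 119/125 (an example with six misses): 95.2%, interval 89.8% to 98.2%

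The first pass is thus far more precise than anything Part 1 can give on sensitivity, and it comes from cases not used in fitting. It describes a narrower group, however: children already scheduled for intervention, whereas the case definition in section 2 also covers disease needing only follow-up.

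**4. Optimism after adjustment.** The SAP gives no adjustment rule, so only a simple case can be worked. If one cutoff is moved down to the lowest of 125 case scores, a new case from the same distribution is equally likely to hold any of the 126 rank positions. The expected miss rate is then 1/126 = 0.8%, against an apparent 0%. The chance that true sensitivity lies below 97.1% is 0.971¹²⁵ = 2.5%, so for this rule the naive lower limit still holds. Wider searches could give more, but any figure would rest on a search rule the SAP does not contain.

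**The case against.** The strongest reply is that the text already implies a proper order. The lowest-AIC model is called final, it is then tried on the Part 2 cases, and it is changed only if some are missed. Misses must be counted for the rule to operate, and updating a model after a failed validation is legitimate. This largely stands. A reader might infer that the first-pass result is discarded or replaced by a tuned 100%; the SAP does not say so. The defect is narrower: reporting that result is not promised, and without a cutoff it has no defined value.

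A reader might also infer that 125 out of 125 will be claimed whatever the first pass showed. The text does not support that either: zero false negatives is worded as an aim, and trying predictor levels as an exploration.

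Third, the optimism may be small. For one moved cutoff it is, as step 4 shows. An optimism of several points would require search rules that the SAP does not state.

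Fourth, the trigger is not certain: above about 99.4% true sensitivity, no adjustment is the likelier outcome. In intervention-level disease, with a cutoff aimed at zero misses, such values cannot be excluded.

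What remains is that the written rule turns the validation set into a tuning set whenever it is used, with nothing fixed beforehand to preserve the validation result.

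**Conclusion.** The concern holds in this form: followed as written, section 6 does not secure the validation that section 1 sets as a main purpose of Part 2. If adjustment is triggered, the adjusted model's sensitivity in these cases is apparent performance. Adjustment is more likely than not at any true sensitivity below about 99.4%.

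The binomial figures assume independent cases and exactly 125 of them. The 0.8-point optimism assumes one moved cutoff and new cases of the same kind. Larger values are hypothetical. The Part 1 ROC curve and NPV are not changed by the Part 2 rule, but they carry their own optimism from selecting variables on about 10 cases.

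This should be fixed before Part 2 data are opened. It does not invalidate the study, because the ordering in the text is compatible with a clean first pass once the missing elements are written down.

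**What to change.** Amend section 6 (Predictor analysis) as follows.

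- State how the Part 1 cutoff is chosen, and lock coefficients and cutoff before Part 2 data are opened.
- Apply the locked model once, unchanged. Always report its Part 2 sensitivity with an exact 95% confidence interval, labelled as sensitivity in known, intervention-level disease.
- Call any later version updated, not validated. Report its sensitivity as apparent or, if the adjustment rule and the levels to be tried are pre-specified, by cross-validation that repeats that rule. Give specificity in Part 1 controls beside it, since a zero-miss cutoff can be bought with false positives that a cases-only sample cannot show.
- Take specificity and NPV from Part 1, since Part 2 contributes no controls. Correct both for optimism by resampling that repeats the p ≤ 0.25 screen and the AIC selection.

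The cost is some extra analysis and the work of writing the rules in advance; no patients or data are added. There is less freedom to react to unforeseen misses, and the validation claim becomes narrower and possibly less favourable. Two limits remain: with about 10 Part 1 cases the corrected figures will be imprecise, and the difference in case mix between Part 2 and murmur referrals is labelled, not removed.

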2. ENDPOINT

Outcome variable

The primary outcome variable in part 1 is a diagnosis of cardiac disease based upon echocardiographic assessment. The diagnostic process will adhere to international consensus guidelines on paediatric cardiology (Doshi & Chikkabryappa, 2018; Sachdeva et al., 2020; Writing Committee et al., 2021). Thereafter, all participants will be assigned to either of two groups: a) A cardiac diagnosis that needs intervention/treatment and/or further clinical follow-up (cases); b) No cardiac diagnosis or a cardiac

Cardiac murmurs in children: Predictive value of cardiac markers (CAMUS)

diagnosis that does not need intervention/treatment and/or further clinical follow-up (controls). Hence, the primary outcome variable is dichotomous. The assignment to cases vs. controls will follow pre-defined criteria pertaining to each cardiac diagnosis/diagnostic group (Table 2).

In part 2, all participants are assigned as cases, as per the inclusion criterium of a confirmed cardiac anomaly in need of intervention.

Table 2. Criteria for assignment of cases (need of intervention and/or clinical follow-up) vs. controls (no need of intervention nor clinical follow-up)	
Primary cardiac diagnosis	Criteria for caseness (only one criterium needs to be fulfilled per diagnosis)
Persistent foramen ovale (PFO)	N/A (never assigned as case)
Atrial septal defect (ASD), all subgroups	Case if: 
 - Ostium premium defect - Sinus venosus defect - Ostium secundum defect diameter > 3 mm OR with signs of right atrium volume load.
Persistent ductus arteriosus (PDA)	Case if: 
 - Ductus diameter >1.5 mm. - LA/Ao ratio >1.5 - Retrograde diastolic flow in the abdominal aorta. - Continuous murmur
Ventricular septum defect (VSD), all subgroups	Case if 
 - Perimembranous location - Inlet location - Subpulmonary outlet/supracristal location - Muscular location with diameter >5 mm OR left ventricular dilatation OR Qp/Qs ≥1.5. - Multiple defects
Aortic valve pathology (stenosis (AS), regurgitation (AR), bicuspid valve)	Case if: 
 - Flow velocity ≥ 2.0 m/s. - Hypertrophy of left ventricle. - Aortic regurgitation (more than trivial)

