3. OTHER VARIABLES

The main analysis is aimed to construct a prediction model for CHD that can be applied in general practice. The analysis will entail bivariate logistic regression between potential predictor (independent) variables and the primary outcome variable (cf. above), followed by multivariable logistic regression modelling and construction of receiver operating curves (ROC).

Relevant predictor (independent) variables include (but are not restricted to):

- *Background*: Sex, age, ethnicity, weight/height
- *Clinical symptoms*: Breathlessness, exertion intolerance/low physical fitness, sweating, reduced general condition
- *Routine clinical findings*: Heart rate, respiratory rate, SaO₂, murmur characteristics, blood haemoglobin,
- *ECG characteristics*: PR interval, QRS interval, QRS axis, Sokolow-index
- *Blood biomarkers*: NT-proBNP, troponin T, hsCRP, IL-6

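### Validation and adjustment of the model are tied to missing no case, with no specificity or referral limit, and part 2 can test sensitivity only

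*SAP*

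**What the plan says.** Section 1 (Design overview) states the role of part 2: "A main purpose of part 2 is to validate the prediction model developed in part 1". Section 2 (Outcome variable) settles who is in it: "In part 2, all participants are assigned as cases, as per the inclusion criterium of a confirmed cardiac anomaly in need of intervention".

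Section 6 (Predictor analysis) says the model is to be "validated by including a total of n~125 individuals with known CHD in the study population". The criterion follows: "The prediction model should correctly classify all these cases; if not, the model will be adjusted". The target is then given: "We aim for zero false negatives". The means of reaching it is that "we will apply different combinations of levels of the identified predictor variables".

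ROC curves and negative predictive value (NPV) are named as measures in sections 4 and 6. The SAP attaches no required specificity, positive predictive value, NPV or referral share to the criterion or to the adjustment. Section 3 gives the intended use: "The main analysis is aimed to construct a prediction model for CHD that can be applied in general practice".

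**The concern.** A rule-out tool for general practice has two properties that matter: it must not miss children with disease, and it must clear a worthwhile share of children without it. The SAP sets a target for the first and none for the second. Its response to a missed case is to change the model, and nothing says when the price in flagged healthy children has become too high.

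The children in part 1 have already been referred for a murmur. A rule that flags nearly all of them would satisfy the stated criterion and change almost nothing in practice. The study could then report a model as validated without having shown that it is useful. Any specificity quoted for it would come from the same controls that were used to select the predictors.

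**Working it through.** **Inputs.** Part 2: about 125 children, all cases (sections 1 and 2). Part 1: about 500 children, prevalence of cardiac disorder 2%, AUC 0.85 for NT-proBNP from a previous study (section 4). This gives about 500 × 0.02 = 10 cases and 490 controls in part 1, before any dropout.

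**The plan's own figures.** The pooled case:control ratio of about 0.25 reproduces as 125/500. Counting the 10 expected part 1 cases as cases gives 135/490 = 0.28. The part 1 sample size also reproduces: a two-sided test of AUC 0.85 against 0.5 at α 0.01 and power 0.80 needs 7.5 cases by the Hanley-McNeil variance. That rounds up to 8, and 8 × 50 = 400; 400/0.8 = 500. Neither figure is in dispute here.

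**Step 1: what the criterion can exclude.** A rule that flags every child classifies 125/125 part 2 cases correctly and misses none, so it meets the criterion. Its specificity is 0/490. This needs no distributional assumption.

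**Step 2: whether NPV would show the problem.** NPV = true negatives / (true negatives + false negatives). With zero false negatives it is 100% whether the rule clears 10 controls (10/10) or 400 (400/400). It is undefined (0/0) only if no child is cleared. NPV therefore cannot separate a useful rule from one that refers nearly everyone. The ROC curve displays the trade-off, but no decision is linked to it.

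**Step 3: how often adjustment would be triggered.** With independent cases and true sensitivity s, the chance that all 125 are classified correctly is s^125.

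| True sensitivity | Chance of no miss in 125 | Chance of adjustment |
|---|---|---|
| 98% | 8% | 92% |
| 99% | 28% | 72% |
| 99.5% | 53% | 47% |

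**Step 4: what 125/125 would show.** The exact two-sided 95% lower bound for sensitivity is 0.025^(1/125) = 97.1%. That holds for a rule fixed before part 2. A rule adjusted until it fits the same 125 children reaches 125/125 by construction.

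**Step 5: illustration of the price.** Assume a single score, controls N(0, 1) and cases N(m, r²), where r is the case:control SD ratio and m = z(AUC) × √(1 + r²). Put the cutoff at the lowest of 125 case scores; specificity is then Φ(minimum case score). Mean over simulations:

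| AUC | SD ratio r | Mean specificity | Controls still flagged |
|---|---|---|---|
| 0.85 | 1.0 | 15% | 85% |
| 0.85 | 0.7 | 30% | 70% |
| 0.85 | 1.3 | 7% | 93% |
| 0.90 | 1.0 | 24% | 76% |
| 0.95 | 1.0 | 41% | 59% |
| 0.98 | 1.0 | 62% | 38% |

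At AUC 0.85 with equal SDs, the 10th to 90th percentile range is 5% to 27%. A mean of 15% corresponds to about 490 × 0.85 ≈ 417 of 490 controls flagged.

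**The case against.** Several points on the other side are fair.

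- **Specificity can be computed.** A reader might infer from the all-case part 2 that the validation has no controls. Sections 4 and 6 do not support that: the 125 cases are added to the part 1 population, so about 490 controls are present. What remains is that they are development data and that the criterion does not refer to them.
- **The adjustment is not literally one falling cutoff.** A reader might infer that the threshold is simply lowered until the last case is caught. The text describes trying combinations of levels of several predictors, which could also improve discrimination. It is open-ended rather than one-directional, but no limit on flagged controls is attached either way.
- **The wording is partly an aim and an exploration.** The SAP sets no formal pass/fail decision. However, the sentence that a model missing a case will be adjusted is directive, and it is the only criterion given for the validation.
- **Priority on missed cases is deliberate.** Section 4 says so, and nothing here disputes it. The point is that the cost should be visible and that there should be a result at which adjustment stops.
- **The illustration is fragile.** AUC 0.85 belongs to one marker in a previous study. A multivariable model may separate better, as may children already scheduled for intervention. The result also depends on the extreme lower tail of an assumed distribution. No single figure can be read as a forecast, and at the higher AUCs the rule would clear a real share of controls.
- **A usefulness limit might stand in the protocol,** which is not at hand. The SAP nevertheless sets the validation criterion itself and sets it on one side only.

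**Conclusion.** The point holds in this form: the SAP ties validation and adjustment to missing no case, sets no specificity or referral limit, and uses a part 2 sample that can inform sensitivity alone. That a rule flagging nearly every child satisfies the criterion follows from the text without modelling. The 72% chance of adjustment at true sensitivity 99% assumes only independent cases.

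The specificity figures are illustrative. Under a binormal score with no miss among 125 cases, mean specificity runs from 7% to 30% at AUC 0.85, depending on the SD ratio, and reaches 62% at AUC 0.98 with equal SDs. A reader might go further and conclude that the validated model will clear almost no healthy child. The documents do not support that, because the final model's AUC and score distribution are unknown. They do show that such a model would not be stopped by the plan. The data stay usable and the repair is cheap, so this is a change that should be made rather than a fatal flaw.

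**What to change.** 1. State in sections 1 and 6 that part 2 validates sensitivity only.
2. For the part 1 model and for every adjusted version, report specificity in the part 1 controls with a 95% CI, always beside sensitivity with a 95% CI and the count of missed cases.
3. Because the controls are development data and any adjustment uses the part 2 cases, correct both measures for optimism by bootstrapping or cross-validating the whole procedure: predictor screening, AIC selection and adjustment.
4. Before part 2 data are opened, record the investigators' own minimum specificity (or maximum referral share). Below it, the conclusion is that no usable rule-out cutoff was found, and adjustment stops. The level is a judgement for the investigators; the documents give no basis for choosing it here.

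The cost is SAP wording, a few table lines and some extra analysis, with no new data. The downside is that the study may have to report that no usable cutoff exists.

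### Part 2 enrols only children scheduled for intervention, so it cannot independently validate the follow-up-only component of the primary case definition

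*SAP*

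**What the plan says.** **Case definition.** SAP Section 2 defines a case as "A cardiac diagnosis that needs intervention/treatment and/or further clinical follow-up (cases"). Table 2 then assigns caseness by anatomical and Doppler criteria for each diagnosis, and most of these do not depend on a planned intervention.

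**Who is in part 2.** Table 1 in Section 1 gives the entry criterion: "Confirmed cardiac anomaly and scheduled for intervention at OUS Rikshospitalet (part 2"). Section 2 draws the consequence: "In part 2, all participants are assigned as cases, as per the inclusion criterium of a confirmed cardiac anomaly in need of intervention".

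**What part 2 is for.** Section 1 states: "A main purpose of part 2 is to validate the prediction model developed in part 1". Section 6 (Predictor analysis) says that about 125 such children are brought into the study population, that the model should classify every one of them correctly, and that it will be adjusted otherwise. The goal follows directly: "We aim for zero false negatives, i.e. all cases with cardiac abnormalities in need of intervention and/or hospital follow-up should be identified".

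**Pooling and planned measures.** Section 4 adds the 125 to the roughly 500 children of part 1 and gives a case-to-control ratio of about 0.25. The full analysis set in Section 5 spans both parts. The named performance measures are ROC curves and negative predictive value.

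**Sensitivity definitions.** Section 6 repeats the analyses with caseness widened to every echocardiographic abnormality (definition 1) and narrowed to those needing surgery or catheter intervention (definition 2).

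**The concern.** The goal covers two kinds of case and the validation sample holds one of them. By its entry criterion part 2 contributes no follow-up-only case, so a perfect result there is silent about that group. Its only members are in part 1, where the model is selected and its cut-offs explored, so how well they are detected there is apparent performance rather than validation.

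Case mix adds to this. Once part 2 is pooled with part 1, intervention cases dominate any ROC curve or sensitivity. If the model finds them more readily than follow-up-only cases, which is plausible for markers of cardiac load but not quantified in the SAP, pooled performance will look better than it would among children referred with a murmur.

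The model is meant for general practice, and the SAP asks for a very low risk of false negatives. The plan should therefore state which kinds of case that assurance covers.

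**Working it through.** **The plan's own figures.** The ratio in Section 4 is 125/500 = 0.25, which counts all of part 1 as controls. With the 10 part 1 cases expected at 2%, it is 135/490 = 0.276. The 500 follows from 400/(1 − 0.20). The 400 is reproduced with the SAP's AUC of 0.85 against an assumed null of 0.5 (Hanley-McNeil variance, two-sided alpha 0.01, power 0.80, 49 controls per case): 7.5 cases, rounded up to 8, plus 392 controls. These figures are not in dispute.

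**Inputs.** From the SAP: 500 children in part 1, 125 in part 2, and for prevalence "the prevalence of cardiac disorder in the population under study is estimated at 2" %. Assumed, because the SAP gives no values:
- detection of intervention cases, s_I = 98%
- detection of follow-up-only cases, s_F = 70%
- half of part 1 cases are follow-up-only
- alternative prevalences of 5%, 10% and 20%, in case the Table 2 criteria capture more children than the register figure suggests

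**Formulas**, with n the number of part 1 cases:
- minimum intervention share of pooled cases = 125/(125 + n)
- pooled sensitivity = [(125 + n/2) × s_I + (n/2) × s_F]/(125 + n)
- sensitivity in the part 1 case mix = (s_I + s_F)/2 = (0.98 + 0.70)/2 = 84.0%

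| Prevalence | n | Minimum intervention share | Pooled sensitivity | Part 1 mix |
|---|---|---|---|---|
| 2% (SAP) | 10 | 125/135 = 92.6% | (130 × 0.98 + 5 × 0.70)/135 = 97.0% | 84.0% |
| 5% | 25 | 125/150 = 83.3% | (137.5 × 0.98 + 12.5 × 0.70)/150 = 95.7% | 84.0% |
| 10% | 50 | 125/175 = 71.4% | (150 × 0.98 + 25 × 0.70)/175 = 94.0% | 84.0% |
| 20% | 100 | 125/225 = 55.6% | (175 × 0.98 + 50 × 0.70)/225 = 91.8% | 84.0% |

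**What drives the gap.** It equals (s_I − s_F) × (follow-up-only share in part 1 − follow-up-only share in the pool).
- At 2%: 0.28 × (0.500 − 5/135) = 0.28 × 0.463 = 13.0 points.
- At 20%: 0.28 × (0.500 − 50/225) = 0.28 × 0.278 = 7.8 points.
- If s_I = s_F, it is zero.

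**With no intervention case missed.** Take s_I = 100% and s_F = 50%, again with half of part 1 cases follow-up-only.
- At 2%: (130 + 2.5)/135 = 98.1% pooled, against 75.0% in the part 1 mix.
- At 20%: (175 + 25)/225 = 88.9%, against 75.0%.

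At the extreme, if all 10 part 1 cases at 2% were follow-up-only and every one was missed, pooled sensitivity would still be 125/135 = 92.6%.

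**Precision when every case is detected.** The exact two-sided 95% lower limit for n of n is 0.025^(1/n).
- Part 2, 125/125: 97.1%, for intervention cases only.
- Follow-up-only cases in part 1: 5/5 gives 47.8% and 10/10 gives 69.2%.

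**The case against.** The strongest reply is that the aim is a count over all cases, not a percentage. Part 1 follow-up-only cases lie inside it, and 125 detected intervention cases cannot hide one miss among them. That is correct: the group is not outside the criterion. It does not amount to validation, however. Section 6 explores combinations of predictor levels to reach zero false negatives, so success in those few children partly reflects tuning. Success is also weak evidence: even with no tuning, a model with a true sensitivity of 70% would detect all of five such cases with probability 0.70^5 = 17%.

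Second, 98% detection does not describe a perfect part 2 result. It implies 125 × 0.02 = 2.5 expected misses and a chance of none of only 0.98^125 = 8%, and any miss would trigger adjustment. This stands, which is why the 100%/50% case is shown as well; the gap remains.

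Third, the SAP names ROC curves and negative predictive value, not a pooled sensitivity. Also true. But pooling is what Sections 4 and 6 describe, zero false negatives is a sensitivity criterion, and a pooled ROC curve carries the same case mix.

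Fourth, sensitivity definition 2 already matches part 2. It does, but it does not limit the claim for the primary definition, and neither definition isolates follow-up-only cases.

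A reader might also infer that half of the case definition goes untested, that pooled performance is bound to be overstated, or that the sponsor will report part 2 as proof for follow-up-only children. The SAP supports none of these. It gives no split between case types, no detection rates by type, and no wording for the eventual report.

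**Conclusion.** The point holds on the SAP's own text: part 2 cannot independently validate the follow-up-only component of the primary case definition, although Section 6 uses it to validate a model whose goal includes that component. This needs no numerical assumption.

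Overstatement of pooled performance is likely rather than certain. It requires follow-up-only cases to be detected less often than intervention cases. With the assumed 98% and 70% and an even split in part 1, the gap is 13.0 points at the SAP's 2% prevalence and 7.8 points at an assumed 20%. Equal detection would remove the gap and still leave follow-up-only cases unvalidated. The minimum intervention share of pooled cases depends on prevalence alone: 93% at 2%, and 83% to 56% at an assumed 5% to 20%.

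**What to change.** In Section 6 (Predictor analysis):

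- State that part 2 validates the model only for cases requiring intervention, which corresponds to sensitivity definition 2, and restrict the part 2 conclusion to them.
- Report sensitivity with exact intervals separately for part 1 follow-up-only cases, part 1 intervention cases and part 2 cases. The split in part 1 is already needed for definition 2: follow-up-only can be defined as meeting the primary definition but not definition 2.
- Do not present a pooled ROC curve or pooled sensitivity as the result for the primary case definition.
- Base any statement about follow-up-only cases on part 1 alone, labelled as development data.

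The cost is SAP wording and one stratified table from data already planned, with no new recruitment. The downside is a narrower validation claim and an imprecise estimate for follow-up-only cases, as the lower limit of 47.8% for 5/5 shows. Independent validation of that group would need a further sample of such children, which is a larger decision for the sponsor.
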